8.3 Immune-Related Response Assessment

Overall response will also be assessed using iRECIST [Seymour 2017]. Immunotherapeutics may result in infiltration of immune cells leading to transient increase in the size in malignant lesions, or undetectable lesions becoming detectable. The criteria are identical to those of RECIST 1.1 in many respects but have been adapted to account for instances where an increase in tumour burden, or the appearance of new lesions, does not reflect true tumour progression.

Key differences are described below. All responses defined using iRECIST criteria are designated with a prefix. iRECIST time-point and best overall responses will be recorded separately.

Confirming Progression

Unlike RECIST 1.1, iRECIST requires the confirmation of progression and uses the terms iUPD (unconfirmed progression) and iCPD (confirmed progression). Confirmatory scans should be performed at least 4 weeks, but no longer than 8 weeks after iUPD.

iCPD is confirmed if further increase in tumour burden, compared to the last assessment, is seen as evidenced by one or more of the following:

- Continued increase in tumour burden (from iUPD) where RECIST 1.1 definitions of progression had been met (from nadir) in target, non-target disease or new lesions
 - Progression in target disease worsens with an increase of at least 5 mm in the absolute value of the sum
 - Continued unequivocal progression in non-target disease with an increase in tumour burden
 - Increase in size of previously identified new lesion (s) (an increase of at least 5 mm in the absolute value of the sum of those considered to be target new lesions) or additional new lesions.
- RECIST 1.1 criteria are met in lesions types (target or non-target or new lesions) where progression was not previously identified, including the appearance of additional new lesions.

If iUPD is not confirmed at the next assessment, then the appropriate response will be assigned (iUPD if the criteria are still met, but no worsening, or iSD, iPR or iCR if those criteria are met compared to baseline). As can be seen in table 2, the prior documentation of iUPD does not preclude assigning iCR, iPR, or iSD in subsequent time-point assessments or as best overall response (BOR) providing that iCPD is not documented at the next assessment after iUPD.

New Lesions

New lesions should be assessed and measured as they appear using RECIST 1.1 criteria (maximum of 5 lesions, no more than 2 per site, at least 10 mm in long axis (or 15 mm in short axis for nodal lesions), and recorded as New Lesions-Target (NLT) and New Lesion-Non-Target (NLNT) to allow clear differentiation from baseline target and non-target lesions.

New lesions may either meet the criteria of NLT or NLNT to drive iUPD (or iCPD). However, the measurements of NLT should NOT be included in the sum of measures of original target lesions identified at baseline. Rather, these measurements will be collected on a separate table in the case record form.

PD is confirmed in the New Lesion category if the next imaging assessment, conducted at least 4 weeks (but not more than 8 weeks) after iUPD confirms further progression from iUPD with either an increase of at least 5 mm in the absolute value of the sum of NLT OR an increase (but not necessarily unequivocal increase) in the size of NLNT lesions OR the appearance of additional new lesions.

				Time Point Response
Target Lesions*	Non-Target Lesions*	New Lesions*	No prior iUPD**	Prior iUPD**; ***
iCR	iCR	No	iCR	iCR
iCR	Non-iCR/Non- iUPD	No	iPR	iPR
iPR	Non-iCR/Non- iUPD	No	iPR	iPR
iSD	Non-iCR/Non- iUPD	No	iSD	iSD
iUPD with no change OR decrease from last TP	iUPD with no change OR decrease from last TP	Yes	NA	NLs confirms iCPD if NLs were previously identified and increase in size (≥5 mm in SOM for NLT or any increase for NLNT) or number. If no change in NLs (size or number) from last TP, remains iUPD
iSD	iUPD	No	iUPD	Remains iUPD unless iCPD confirmed based in further increase in size of NT disease (need not meet RECIST 1.1 criteria for unequivocal PD)
iUPD	Non-iCR/Non- iUPD	No	iUPD	Remains iUPD unless iCPD confirmed based on:further increase in SOM of at least 5 mm, otherwise remains iUPD
iUPD	iUPD	No	iUPD	 Remains iUPD unless iCPD confirmed based on further increase in: previously identified T lesion iUPD SOM ≥5 mm and / or NT lesion iUPD (prior assessment - need not be unequivocal PD)
iUPD	iUPD	Yes	iUPD	 Remains iUPD unless iCPD confirmed based on further increase in: previously identified T lesion iUPD ≥5 mm and / or previously identified NT lesion iUPD (need not be unequivocal) and /or size or number of new lesions previously identified
Non- iUPD/PD	Non-iUPD/PD	Yes	iUPD	 Remains iUPD unless iCPD confirmed based on increase in size or number of new lesions previously identified
* Using REC same.	IST 1.1 principles. If	no PSPD oc	curs, RECIST 1	1 and iRECIST categories for CR, PR and SD would be the

Table 4: Time-point (TP) iResponse

** In any lesion category.

*** Previously identified in assessment immediately prior to this TP.

Table 5: iRECIST Best Overall Response (iBOR)

TPR1	TPR2	TPR3	TPR4	TPR5	iBOR	
iCR	iCR, iPR, iUPD, NE	iCR, iPR, iUPD, NE	iUPD	iCPD	iCR	
iUPD	iPR, iSD, NE	iCR	iCR, iPR, iSD, iUPD, NE	iCR, iPR, iSD, iUPD, iCPD, NE	iCR	
iUPD	iPR	iPR, iSD, iUPD, NE	iPR, iSD, iUPD, NE, iCPD	iPR, iSD, iUPD, NE, iCPD	iPR	
iUPD	iSD, NE	PR	iPR, iSD, iUPD, NE	iPR, iSD, iUPD, iCPD, NE	iPR	
iUPD	iSD	iSD, iUPD, NE	iSD, iUPD, iCPD, NE	iSD, iUPD, ICPD, NE	iSD	
iUPD	iCPD	Anything	Anything	Anything	iCPD	
iUPD	iUPD	iCPD	Anything	Anything	iCPD	
iUPD	NE	NE	NE	NE	iUPD	

All patients will have their iBOR from the start of study treatment until the end of treatment classified as outlined below.

• Table assumes a randomized study where confirmation of CR or PR is not required.

• NE = not evaluable that cycle.

• Designation "I" for BOR can be used to indicate prior iUPD to aid in data interpretation.

• For patients with non-target disease only at baseline, only CR or non-CR/non-PD can be assigned at each TPR but is not shown in the table for ease of presentation.

8.4 Response Duration (RECIST 1.1 and iRECIST)

Response duration will be measured from the time measurement criteria for CR/PR or iCR/iPR (whichever is first recorded) are first met until the first date that recurrent or progressive disease is objectively documented, taking as reference the smallest measurements recorded on study (including baseline).

8.5 Stable Disease Duration

Stable disease duration will be measured from the time of start of registration until the criteria for progression are met, taking as reference the smallest sum on study (including baseline).

8.6 Methods of Measurement

The same method of assessment and the same technique should be used to characterize each identified and reported lesion at baseline and during follow-up. Assessments should be identified on a calendar schedule and should not be affected by delays in therapy. While on study, all lesions recorded at baseline should have their actual measurements recorded at each subsequent evaluation, even when very small (e.g. 2 mm). If it is the opinion of the radiologist that the lesion has likely disappeared, the measurement should be recorded as 0 mm. If the lesion is believed to be present and is faintly seen but too small to measure, a default value of 5 mm should be assigned. For lesions which fragment/split add together the longest diameters of the fragmented portions; for lesions which coalesce, measure the maximal longest diameter for the "merged lesion".

8.6.1 Clinical Lesions

Clinical lesions will only be considered measurable when they are superficial and ≥ 10 mm as assessed using calipers (e.g. skin nodules). For the case of skin lesions, documentation by colour photography including a ruler to estimate the size of the lesion is recommended. If feasible, imaging is preferred.

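### Table 4's last row keeps iUPD where the Section 8.3 text confirms iCPD: a first new lesion after target or non-target iUPD

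*Combined protocol and SAP*

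**What the plan says.** Section 8.3, Confirming Progression, lets iCPD be "evidenced by one or more of the following". The first item is worsening in disease that was already progressing. The second is that "RECIST 1.1 criteria are met in lesions types (target or non-target or new lesions) where progression was" not identified before. Section 8.2.5 makes the appearance of a new lesion progression in its own right, and the New Lesions paragraph of 8.3 allows new lesions to drive iCPD as well as iUPD.

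Table 4 turns this into time-point calls. Its last row has neither target nor non-target disease progressing and new lesions present. The call after a prior iUPD is "Remains iUPD unless iCPD confirmed based on increase in size or number of new lesions previously identified". The footnotes to that column set its scope: the prior iUPD may be "In any lesion category", and it is one "Previously identified in assessment immediately prior to this TP".

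Section 8.2.5 sends the reader to Table 4 to decide when progression is unequivocal. On best response, Section 8.3 lets a later iCR, iPR or iSD count after iUPD, "providing that iCPD is not documented at the next assessment after iUPD".

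**The concern.** Two investigators reading the same pair of scans could each follow Section 8.3 faithfully and record different calls. The documents do not say whether the text or the table takes precedence.

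The label is used elsewhere:
- Section 5.0, footnote 10, runs off-treatment scans until relapse or iCPD, for up to two years.
- Section 10.4 ends routine follow-up for patients who leave treatment with iCPD. It keeps follow-up and a confirmatory scan for those who leave with iUPD.
- Section 10.1 continues clinically stable iUPD patients to the next assessment, and Section 10.2 stops treatment at unequivocal progression.
- Table 5 fixes best overall response at iCPD once iUPD is followed by iCPD, whatever comes later. A patient left at iUPD can still be credited with a later response or stable disease under the 8.3 text.

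**Working it through.** The plan gives no figure to reproduce here. The check traces one set of findings through both rules.

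**Illustrative case (sizes assumed).** Nadir target sum 50 mm, no new lesions so far.
- Scan 1: target sum 61 mm. (61 − 50)/50 = 22%, absolute increase 11 mm. This meets the 8.2.5 rule (at least 20% and more than 5 mm), so target iUPD.
- Scan 2, the next assessment: target sum 58 mm. (58 − 50)/50 = 16%, below 20%, so target disease no longer meets PD. Non-target disease is not progressing. A first new lesion of 12 mm appears.

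| Rule | Reasoning at scan 2 | Call |
|---|---|---|
| 8.3 text, second item | New lesions were not progressing at scan 1 and now meet RECIST 1.1 progression; one item is enough | iCPD |
| Table 4, last row, prior-iUPD cell | No new lesion had been identified before, so the exception is not met | iUPD |

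The same result follows if the prior iUPD was in non-target disease, or in both.

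**How much of the last row is affected.** Read the row label as neither iUPD nor PD. The prior iUPD can be any non-empty combination of target, non-target and new lesions: 2³ − 1 = 7. Three contain no prior new lesion (target; non-target; both), and there the rules conflict. In the other four a new lesion was already present, so the text and the table use the same route. These are counts of patterns, not patient frequencies.

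**Other rows.**
- Non-target-only row (target iSD, non-target iUPD, no new lesion): confirmation needs a further increase in non-target disease and is not limited to lesions identified before. A first non-target progression after target iUPD can satisfy it.
- Target-only row (target iUPD, no new lesion): confirmation needs at least 5 mm more in the target sum. Newly met target PD usually satisfies this, but not always. Suppose the prior iUPD was non-target with a target sum of 58 mm (+16% on nadir), and the next sum is 61 mm (+22%, +11 mm). Target PD is newly met, yet the rise since the last scan is 61 − 58 = 3 mm. The text gives iCPD; the row gives iUPD.
- Fifth row (target and non-target iUPD unchanged or smaller, new lesions present): "NLs confirms iCPD if NLs were previously identified and increase in size" or number, and iUPD stays if new lesions have not changed. Going from none to one is a change, so the row neither confirms iCPD nor assigns iUPD. It is silent.
- Target progression plus new lesions, and non-target progression plus new lesions, have no row if the last row's label means neither iUPD nor PD. If it means non-iUPD or PD, the last row takes them in with the same restriction.

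**The case against.** The best reconciling argument is that the last row accepts an increase in number. Number can rise only through lesions not seen before, so a first lesion might count as a rise from zero to one. That would bring the table into line with the text. It is strained: the cell ties the increase to new lesions already identified, and with none identified there is nothing to increase. Limiting the column to prior iUPD from new lesions also fails, because its footnote extends it to every lesion category.

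It is also argued that Sections 8.1.2 and 8.3 adopt a published guideline which may settle the case. That guideline is not part of the documents. The protocol has to work as written, and it points to Table 4.

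The objections to wider readings do stand. A reader might infer that Table 4 as a whole omits confirmation in a newly progressing category. It does not: the target-only and non-target-only rows usually permit it, and the fifth row is silent. A reader might infer a delay of 4 to 8 weeks in declaring iCPD. That is not assured: Section 10.1 only recommends the 8-week limit, routine imaging is every 12 weeks, and a later scan may never confirm. A reader might also infer longer treatment. Section 10.1 encourages continuing treatment in mixed responses, and Section 10.2 accepts clinical as well as radiographic evidence of progression.

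On best response, the effect needs a later iSD, iPR or iCR, and Table 5 shows no sequence of two iUPD calls followed by response. The route is through the 8.3 text.

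**Conclusion.** The last row of Table 4 is wrong as written for one defined sequence: iUPD in target and/or non-target disease, then a first new lesion at the next assessment with target and non-target disease no longer progressing. The 8.3 text calls this iCPD; the table calls it iUPD. The remaining rows are unclear in places rather than contradictory throughout.

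The consequence is limited to the iUPD/iCPD label, iRECIST best overall response and the follow-up rules tied to iCPD. Section 13 names no iRECIST analysis. The primary endpoint in Section 13.2 is response by RECIST 1.1, so the response rate, alpha, power and sample size are untouched. In the example, scan 1 is already RECIST 1.1 progression, so a progression date on that basis is set before the disputed scan.

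The conclusion assumes that the words limiting the cell to lesions already identified mean what they say, and that footnoted scope applies to the whole column. The number of patients affected cannot be estimated from the documents. The correction should be made because it is cheap and makes the recorded calls reproducible.

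**What to change.** 1. Add to the last row's prior-iUPD cell: *or iCPD if new lesions appear for the first time after iUPD in target or non-target disease*.
2. State in Section 8.3 that the Confirming Progression text governs wherever Table 4 differs from it or has no row. This also settles the target-only edge case, the silent fifth row and the two combinations without an unambiguous row.
3. Re-check recorded iRECIST calls for patients with iUPD followed by a first new lesion, where the data allow. Target values are recorded at each assessment (Section 8.2.3) and new target-lesion measurements are kept in a separate table (Section 8.3). Non-target lesions are followed only as present or absent (Section 8.2.4), so some calls resting on non-target progression may not be recoverable.

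The cost is a wording change and the re-check; no extra scans or patients. Whether the eCRF needs changing cannot be judged from the documents.

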I understand that I may terminate or suspend enrollment of the study at any time if it becomes necessary to protect the best interests of the study subjects, however I will give prompt notice to CCTG. The study may be terminated at any time by CCTG or AstraZeneca with or without cause.

[figure not shown]
Qualified Investigator (printed name and signature) Date

Protocol Number: CCTG IND.228

CENTRE:

TREATMENT SCHEMA

This is a multi-centre, non-blinded, open-label single arm phase II study of durvalumab in combination with tremelimumab in patients with rare tumours. A minimum of 80, and a maximum of 160 patients will be enrolled.

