- 9 To ensure comparability, baseline scans and subsequent scans to assess response must be performed using identical technique (i.e. scans performed immediately following bolus contrast administration using a standard volume of contrast, the identical contrast agent, and preferably the same scanner). Maintain schedule every 12 weeks even if cycles are delayed. For osteosarcoma patients, every 3 months if bone mets are present at baseline. For patients remaining on study beyond January 2022, the frequency of imaging assessment may be reduced to every 6 months at the description of the investigator and discussion with CCTG.
- 10 To be done every 12 weeks until relapse or progression (iCPD) for up to 2 years, for patients with CR/iCR, PR/iPR, SD/iSD response as defined in Section 8. Patients with CR/iCR or PR/iPR or equivocal PD (pseudoprogression)/iUPD should have scans repeated after 4 weeks, but no more than 8 weeks, to confirm response.
- 11 Depending on histology, applicable markers (i.e. CA-125 for the Clear Cell Carcinoma of the Ovary cohort) must be reported as per standard of care at local sites.
- 12 Only if significant cardiac history (see section 4.2.6).
- 13 Must be confirmed available prior to registration on ALL patients. Archival tissue submission should be sent at the same time that the baseline CRF is submitted for each patient. Prescreening of TIL and PDL1 expression is required for cohort 2 patients prior registration. See Section 12.0 for details.
- 14 After registration but before the first dose of study treatment. See lab manual for details.

5.1 Follow-up for Ineligible or Patients That Go Off Study Prior to Starting Protocol Therapy

The follow-up requirements for ineligible patients/patients who have received no protocol therapy prior to going off study include submission of the Baseline Report plus an End of Treatment Report. Data submission for ineligible participants who have received at least one dose of protocol therapy should be followed according to the protocol to allow for treatment and adverse event assessment.

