After baseline, a value should be provided on the CRF for all identified target lesions for each assessment, even if very small. If extremely small and faint lesions cannot be accurately measured but are deemed to be present, a default value of 5 mm may be used. If lesions are too small to measure and indeed are believed to be absent, a default value of 0 mm may be used.

8.2.4 Non-target Lesions

All non-measurable lesions (or sites of disease) plus any measurable lesions over and above those listed as target lesions are considered non-target lesions. Measurements are not required but these lesions should be noted at baseline and should be followed as "present" or "absent".

8.2.5 Response.

All patients will have their BEST RESPONSE from the start of study treatment until the end of treatment classified as outlined below:

All patients will have their BEST RESPONSE from the start of study treatment until the end of treatment classified as outlined below:

Complete Response (CR): disappearance of *target* and *non-target* lesions and normalization of tumour markers. Pathological lymph nodes must have short axis measures < 10mm (Note: continue to record the measurement even if < 10mm and considered CR). Residual lesions (other than nodes < 10mm) thought to be non-malignant should be further investigated (by cytology specialized imaging or other techniques as appropriate for individual cases [ref RECIST 1.1]) before CR can be accepted. Confirmation of response is only required in non-randomized studies.

Partial Response (PR): at least a 30% decrease in the sum of measures (longest diameter for tumour lesions and short axis measure for nodes) of target lesions, taking as reference the baseline sum of diameters. Non target lesions must be non-PD. Confirmation of response is only required in non-randomized studies. Patients with CR/iCR or PR/iPR should have scans repeated after 4 weeks, but no more than 8 weeks, to confirm response.

Stable Disease (SD): Neither sufficient shrinkage to qualify for PR nor sufficient increase to qualify for PD taking as reference the smallest sum of diameters on study.

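### Table 5 classifies iRECIST best overall response on a randomised-study, no-confirmation assumption that this single-arm trial does not meet (minor)

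*Combined protocol and SAP*

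**What the plan says.** The Treatment Schema describes an "open-label single arm phase II study", and Section 13.1 speaks of one treatment arm.

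Section 8.3 sets the scope of the iRECIST classification: "All patients will have their iBOR from the start of study treatment until the end of treatment classified as outlined below". Table 5 is the only iBOR classification given. Its note says: "Table assumes a randomized study where confirmation of CR or PR is not required".

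On confirmation, the RECIST 1.1 definitions of CR and PR in Section 8.2.5 each state: "Confirmation of response is only required in non-randomized studies". The PR definition adds: "Patients with CR/iCR or PR/iPR should have scans repeated after 4 weeks, but no more than 8 weeks, to confirm response". Footnote 10 of the Section 5.0 flowsheet repeats the instruction, again naming the iRECIST categories: "Patients with CR/iCR or PR/iPR or equivocal PD (pseudoprogression)/iUPD should have scans repeated after 4 weeks", with the same 8-week limit.

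Section 13.2 defines the primary endpoint by RECIST 1.1 best response, with CR or PR sustained for 4 weeks or longer. Section 8.3 has the iRECIST time-point and best overall responses recorded separately from those under RECIST 1.1.

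**The concern.** The trial asks for scans to confirm an iCR or iPR, then classifies the patient by a table in which a failed confirmation does not remove the response. The table states a premise, randomisation, that this trial does not meet, and no rule adapted to a single arm follows it.

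What is at stake is the meaning of iBOR beside the RECIST 1.1 result. Section 8.3 adapts the criteria to allow for apparent progression that is not real. If iBOR also drops confirmation of response, a gap between the two sets of results mixes two causes, and a reader cannot separate them.

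**Working it through.** **1. The plan's own figures, to fix the scope.** For each cohort (10 + 10 patients, stop at 0/10, active if 4 or more of 20 respond), the probability of declaring activity at true rate p is the sum over x = 1 to 10 of b(x; 10, p) × P(Bin(10, p) ≥ 4 − x).

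| True rate | Quantity | Computed | Stated in Section 13.2 |
|---|---|---|---|
| 5% | declared active | 0.0153 | 0.02 |
| 25% | declared active | 0.7622 | 0.76 |
| 10% | declared ineffective | 1 − 0.1285 = 0.8715 | 0.87 |
| 30% | declared active | 0.8830 | 0.88 |

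The stated figures reproduce. The responders they count are RECIST 1.1 responders; iBOR does not enter.

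**2. The premises side by side.** Table 5 assumes a randomised study without confirmation. The trial has one arm. Section 8.2.5 attaches required confirmation to non-randomised studies, in the RECIST 1.1 definitions. For iCR and iPR the wording is that scans should be repeated to confirm. The strength of the wording differs, but both point towards confirmation and Table 5 points away from it.

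**3. What the rows accept.** I read the PR entry in row 4 as iPR. For each row that ends in iCR or iPR, multiply the entries allowed at each assessment, then count the patterns with only one iCR or iPR before any iCPD.

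| Row | iBOR | Patterns allowed | With a single response |
|---|---|---|---|
| 1 | iCR | 4 × 4 × 1 × 1 = 16 | 2 × 2 = 4 |
| 2 | iCR | 3 × 1 × 5 × 6 = 90 | 2 × 1 × 3 × 4 = 24 |
| 3 | iPR | 1 × 4 × 5 × 5 = 100 | 3 × 4 × 4 + 3 = 51 |
| 4 | iPR | 2 × 1 × 4 × 5 = 40 | 2 × 1 × 3 × 4 = 24 |
| Total | | 246 | 103 |

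Row 1 always starts with iCR and the other three with iUPD, so the first assessment adds a factor of 1. The extra 3 in row 3 are patterns in which an iPR appears only after iCPD. These are counts of permitted patterns, not patient frequencies. They show only that every one of the four rows counts a response seen once.

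**4. The clearest case.** Row 1 permits iCR, iUPD, iUPD, iUPD, iCPD and returns iCR. No later assessment repeats the response. If the scan at 4 to 8 weeks is the one showing iUPD, the CR was not sustained as Section 13.2 requires, so it is not a CR for the primary endpoint. The progression ends confirmed, so there was no pseudoprogression. The two classifications differ only because Table 5 does not ask for confirmation.

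**5. The size.** The effect is the proportion of patients with an unconfirmed iCR or iPR. The documents give no such proportion and nothing from which to derive one.

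**The case against.** The best defence is that the protocol, read as a whole, already carries confirmation over. Section 8.3 says iRECIST matches RECIST 1.1 in many respects and then sets out the key differences; the only one about confirmation concerns progression. On that reading the Table 5 note merely discloses a simplification. Another note to the table admits that one case is left out for ease of presentation, so the table is not a full algorithm. This stands as a reason to call the point minor. It does not remove the conflict, because the scope sentence sends all patients to this table and no adapted rule follows. Section 8.1.2 warns that confirmatory-scan requirements differ between the criteria, but the difference that Section 8.3 describes is about progression, so it does not account for the note.

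A reader might also infer more than the documents support:

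- **That Table 5 contradicts the Table 4 footnote**, by which, without pseudoprogression, the RECIST 1.1 "and iRECIST categories for CR, PR and SD would be the" same. That footnote marks the lesion columns of a time-point table. It does not speak of best overall response or its confirmation.
- **That rows 2 to 4 show the same divergence from RECIST 1.1 as row 1.** They start with iUPD, where RECIST 1.1 progression criteria have been met, so such a patient would ordinarily already have PD. The difference there comes from how iRECIST handles iUPD.
- **That patients who start with iPR or iSD cannot be classified**, since seven rows start with iUPD and one with iCR. The ordinary rules of Section 8.2.5 cover them.

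**Conclusion.** Wrong as written, but minor. Table 5 states an assumption that this trial does not meet, and followed literally it credits iCR or iPR to a response seen once. For the sequences listed in the table, dropping confirmation can only add responders relative to a rule that requires it. By how many cannot be said from the documents.

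It would be tempting to read this as inflating the primary response rate or the false-positive risk of the 4-of-20 rule. The documents do not support that: both rest on RECIST 1.1 responses sustained for 4 weeks or longer. No stated objective and no analysis in Section 13 uses iBOR. The point matters only if iBOR is derived and shown beside the RECIST 1.1 result.

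The conclusion assumes that Table 5 is applied as printed and that the PR entry in row 4 means iPR. It does not depend on which category an unconfirmed response should fall back to, which the documents do not say.

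**What to change.** Before iBOR is derived or reported:

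1. Replace the randomised-study note with a statement that in this single-arm trial an iBOR of iCR or iPR needs confirmation on a repeat assessment at least 4 weeks later, as for RECIST 1.1.
2. Amend the four iCR/iPR rows so that an unconfirmed iCR or iPR is not counted as a response. State the fallback category as a chosen convention, for example iSD where the Table 3 minimum for SD (at least 4 weeks from baseline) is met.
3. State whether a scan after the 8-week limit may confirm. Flowsheet footnote 9 says "Maintain schedule every 12 weeks even if cycles are delayed", so a routine scan 12 weeks after the response falls outside the 4-to-8-week window of footnote 10 and Section 8.2.5. Those passages need to be reconciled with whatever is chosen.

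Alternatively, if an unconfirmed iBOR is intended, label it as unconfirmed, say so where iCR and iPR scans are described, and do not compare it directly with the confirmed RECIST 1.1 rate.

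The cost is one note replaced, four rows amended and two short statements added. No new scans are needed, since iBOR can be re-derived from time-point responses already recorded. The iRECIST response count may be lower.
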